9.3 Sample Size and Power Considerations

A total sample size of 399 subjects (266 subjects for CC-93538 and 133 subjects for placebo) with a 20% dropout rate at the end of the Induction Phase (212 subjects for CC-93538 and 106 subjects for placebo) will provide at least 90% power to detect a difference of -2.79 change in DD from

baseline at Week 24 and at least 90% power to detect a difference of 15% at Week 24 in histologic response with a two-sided significance level (alpha) of 0.05. These calculations were based on a 2 sample t-test assuming a pooled standard deviation of 4.76 for change in DD from baseline and the chi-square test to compare the difference in 2 independent proportions for the histologic response assuming that the true placebo response proportion is 0.05.

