The following sensitivity analyses will be performed to support the main estimand analysis and provide additional insights to understand the treatment effect:

- Robustness due to missing data MI under MAR assumption will be explored using tipping point analysis ([Yan, 2009](#); [Campbell, 2011](#); [Yuan, 2014](#)).
- A minimum of 4 measurable diary days per week is required to derive a DD score for the 14-day period. The analysis method will be the same as the primary analysis.

In considering the ICEs of study interest (ie, ICE number 2, use of rescue therapy/prohibited medication), supplementary analyses will be performed using the treatment policy estimand strategy and a hypothetical estimand strategy. In addition to the overall population, change in DD from baseline to Week 24 will be analyzed in the Steroid Inadequate Responders/Intolerant subgroup. This analysis will be similar to the overall population except that the ANCOVA model will not include Steroid Inadequate Responders/Intolerant status. See Section [9.6.4](#) for details on the hierarchical testing procedure to control the Type I error rate.

9.6.1.3 *Eosinophilic Histologic Response at Week 24 (Induction Phase)*

The other co-primary endpoint, eosinophilic histologic response, is defined as a peak esophageal eosinophil count $\leq 6/\text{hpf}$ (across all available esophageal levels) at Week 24.

The primary analysis of the eosinophilic histologic response will be conducted on the ITT population using the CMH test at a 2-sided 5% significance level, stratified by Steroid Inadequate Responders/Intolerant status. For treatment comparison between CC-93538 360 mg SC once weekly and placebo, the 2-sided 95% CI for the difference in proportions using the CMH weights and the 2-sided p-value from the CMH test will be provided.

Missing data in subjects without use of rescue therapy/prohibited medication prior to Week 24 will be handled using a multiple imputation (MI) approach ([SAS Institute, 2015](#)) under a missing at random (MAR) assumption.

A sensitivity analysis will be performed using tipping point analysis to assess the robustness of the primary efficacy analysis with regards to handling of missing data.

In considering the ICEs of study interest (ie, ICE number 2, use of rescue therapy or prohibited medication which may impact the efficacy assessment), a supplementary analysis using the treatment policy estimand strategy for the histologic endpoint at Week 24 will be conducted.

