In addition to the overall population, histologic response at Week 24 will be analyzed in the Steroid Inadequate Responders/Intolerant subgroup. This analysis will be similar to the overall population except that the analysis will be done using the chi-square test. See Section [9.6.4](#) for details on the hierarchical testing procedure to control the Type I error rate.

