9.6.3 Analysis of Secondary Efficacy Endpoints

End of Maintenance Phase (Week 48):

Histologic Response: The analysis of the histologic response endpoint will be conducted on the ITT population using the CMH test stratified by Steroid Inadequate Responders/Intolerant status. For treatment comparison between a CC-93538 dose and placebo, the 2-sided 95% CI for the difference in proportions using the CMH weights will be provided. Missing data will be handled via the same strategy as for the primary analysis of the co-primary endpoint of histologic response.

Mean change in DD: For the analysis of change in DD from baseline at Week 48, the baseline is defined as the last visit prior to receiving any dose of CC-93538 360 mg or placebo in the Induction Phase. The analysis of change in DD from baseline at Week 48 will be conducted using an ANCOVA model with treatment group (CC-93538 360 mg SC once weekly, CC-93538 360 mg SC once every other week, and placebo), Steroid Inadequate Responders/Intolerant status (yes or no), and baseline DD values included in the model. Point estimates for the mean difference between the treatment groups using the adjusted LS Mean changes and corresponding 95% Wald

CI will be reported. Missing data will be handled via the same strategy as for the primary analysis of the co-primary endpoint of change in DD.

[figure not shown]
In addition to the overall population, histologic response at Week 48 and change in DD from baseline to Week 48 will be analyzed in the Steroid Inadequate Responders/Intolerant subgroup. These analyses will be similar to the overall population except that the analysis will be done using the chi-square test and the ANCOVA model will not include Steroid Inadequate Responders/Intolerant status. See Section 9.6.4 for details on the hierarchical testing procedure to control the Type I error rate.

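### Histologic response is tested without the baseline eosinophil count already collected on every subject: a modest, cheap efficiency gain left unused, not an error

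*Combined protocol and SAP*

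**What the plan says.** Section 9.6.1.3 tests histologic response on the ITT population "using the CMH test at a 2-sided 5% significance level, stratified by Steroid Inadequate Responders/Intolerant status". For the SIR-I subgroup it says that "the analysis will be done using the chi-square test". Section 9.6.2 carries the co-primary method over to the <15/hpf key secondary endpoint. Section 9.6.3 analyses histologic response at Week 48 "using the CMH test stratified by Steroid Inadequate Responders/Intolerant status", again with chi-square in SIR-I. The only further histologic analyses listed for the co-primary are a tipping-point analysis and a treatment-policy analysis; neither adds a covariate.

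The endpoints analysed by ANCOVA are treated differently. Change in DD (Section 9.6.1.2) and the EREFS, EoEHSS grade, EoEHSS stage and mDSD composite scores (Section 9.6.2) each include their own baseline value.

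The baseline count is available. Inclusion Criterion 2 requires a central histology reading before randomization, with a peak of at least 15/hpf at two levels and no upper limit. Section 6.4.1 has the central laboratory enumerate the peak count.

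For planning, Section 9.3 claims "at least 90% power to detect a difference of 15% at Week 24 in histologic response", "assuming that the true placebo response proportion is 0.05". The calculation used "the chi-square test to compare the difference in 2 independent proportions for the histologic response".

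**The concern.** Response is an absolute threshold, while subjects may enter at any peak of 15/hpf or more. Someone starting at a high count has further to fall, so the baseline count is plausibly prognostic. If it is, a test that ignores it gives up some precision on a co-primary endpoint.

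The loss would matter more later in the testing sequence. Section 9.6.4 makes each result confirmatory only if every earlier hypothesis was significant. The sequence includes two Week 48 endpoints and the SIR-I subgroup. At Week 48 the two active regimens are compared with placebo separately (Section 2, Table 3), so the 2:1 pooling of Week 24 is lost. In SIR-I only about 70% of subjects contribute.

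**Working it through.** **Inputs from the documents.** Section 9.3: 266 vs 133 randomized; 212 vs 106 after 20% dropout at the end of Induction; response 0.05 on placebo and 0.05 + 0.15 = 0.20 on active; two-sided alpha 0.05. Section 7.3: about 70% SIR-I.

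**Assumptions, not in the documents.** The correlation between baseline count and outcome; the same 0.20 vs 0.05 rates in SIR-I and at Week 48; how much information is lost by Week 48.

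**1. The plan's own figure.** Power = Φ[(|p1 − p0| − 1.96·s0)/s1], where s0² = p̄(1 − p̄)(1/n0 + 1/n1) and s1² = p0(1 − p0)/n0 + p1(1 − p1)/n1. With n0 = 106 and n1 = 212: p̄ = 0.15, s0 = 0.0425, s1 = 0.0347, and (0.15 − 0.0833)/0.0347 = 1.92. Power is 97.3%, so the stated minimum of 90% is reproduced.

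**2. Validity of the CMH test.** In 4,000 simulated trials per setting (212 vs 106, strata 70/30), type I error was 4.5-5.2% for CMH and 4.9-5.4% for a baseline-adjusted logistic score test. Monte Carlo SE is about 0.34 points.

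**3. Variance saved.** Trials were simulated with a latent-normal count at 20% vs 5% response. The standardised risk difference from a logistic model was compared with the raw difference:

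| Assumed correlation | Variance ratio, 266 vs 133 | Variance ratio, 74 vs 74 |
|---|---|---|
| 0.2 | 0.99 | 1.00 |
| 0.3 | 0.97 | 0.97 |
| 0.4 | 0.95 | 0.95 |
| 0.5 | 0.92 | 0.91 |

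Repeat runs moved these by about 0.01-0.02. There was no material loss at zero correlation. A ratio of 0.97 is worth 399/0.97 − 399 ≈ 12 subjects, and 0.92 is worth 399/0.92 − 399 ≈ 35.

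**4. Week 24 overall.** Dividing the evaluable numbers by the ratios 0.99, 0.97, 0.95 and 0.92 moves 97.3% to 97.4%, 97.7%, 97.9% and 98.3%. A direct simulation, with log-odds slopes of 0, −0.5, −1.0 and −1.5 per SD of baseline, gave CMH 97.9%, 97.9%, 97.7% and 97.1%, against 97.8%, 98.3%, 98.8% and 99.1% adjusted. The gain is 0 to about 2 points.

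**5. Smaller comparisons, unadjusted, same rates.**
- Week 24 SIR-I, 148 vs 74 (0.7 × 212, 0.7 × 106): 88.7%.
- Week 48 overall, 106 vs 106: 91.6%.
- Week 48 SIR-I, 74 vs 74: p̄ = 0.125, s0 = 0.0544, s1 = 0.0530; 79.4%.
- Week 48 SIR-I with every randomized subject fully informative, 93 vs 93 (0.7 × 133): 87.8%.

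**6. Week 48 SIR-I after adjustment.** At ratios 1.00, 0.97, 0.95 and 0.91, 74 per arm gives 79.4%, 80.6%, 81.4% and 83.1%; 93 per arm gives 87.8%, 88.7%, 89.4% and 90.6%. The scaling gives 0 to about 4 points. Allowing for simulation error and the approximate scaling, about 0-5 is a fair range.

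**7. How often the model fails.** At 74 per arm the logistic fit failed in about 2% of simulated trials. That is close to the chance of no placebo responders at all, 0.95^74 = 2.2%.

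**The case against.** The strongest case against is that this is a method preference. CMH is valid under randomization and yields the summary measure named in Table 8, a difference in proportions. That stands.

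Four stronger readings are tempting, and the documents do not support them:

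- **The plan contradicts itself by adjusting some endpoints and not others.** It is consistent by endpoint type: continuous change scores get ANCOVA with baseline, and histologic responses get CMH or chi-square.
- **Chance imbalance in baseline counts biases the test.** The error rate of a randomized comparison already allows for chance imbalance. Only precision is lost.
- **The trial is underpowered at 79.4% for Week 48 SIR-I.** The documents state no power there. The figure carries Week 24 rates and dropout forward and drops missing subjects, whereas Section 9.6.3 uses ITT with multiple imputation. The 87.8% figure is an upper bound, because imputation does not recover all lost information. A larger effect would also change the picture: 25% vs 5% at 74 per arm gives about 93%.
- **The imputation model omits the baseline count.** Its covariates are not stated, and Section 9.1 leaves further detail to the SAP, whose text is not in the supplied document. This is unstated detail, not a shown omission.

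Two practical objections also stand. No correlation is documented, and at 0.2 the gain is close to nil. The model is also least stable where the gain is largest: about 4 placebo responders are expected among 74 (0.05 × 74 = 3.7). An imprecise fallback would be a data-dependent choice of test within a confirmatory sequence.

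The Figure 2 schematic is not shown in the text supplied, so what a failure at Week 48 SIR-I would stop cannot be checked.

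**Conclusion.** The point holds as a missed efficiency of low severity. A prognostically plausible baseline measurement, collected on everyone before randomization, is left out of all the histologic response tests, and using it would keep the estimand. The co-primary test is valid and its power statement is correct.

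The variance saving of about 0-8% rests entirely on assumed correlations of 0.2 to 0.5. The power gain is under about 2 points where power is already 97.3%. It is about 0-5 points at Week 48 in SIR-I, from a starting point of roughly 79-88% that itself assumes the Week 24 planning rates carry over. A weaker correlation would leave almost no gain, but also no material loss.

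**What to change.** Before unblinding, pre-specify in the SAP for histologic response (6/hpf or less and <15/hpf, Weeks 24 and 48, overall and SIR-I):

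1. A logistic model with treatment, steroid stratum (overall population only) and log baseline peak eosinophil count. Report the standardised (marginal) risk difference with its 95% CI. An adjusted odds ratio would be a different estimand and should not replace it.
2. The variance method, and how results are combined across imputed datasets.
3. The current CMH/chi-square analysis as a sensitivity analysis.
4. An exact fallback that makes no reference to the estimated treatment effect. For example: use CMH/chi-square if the model fails to converge or shows separation in any imputed dataset.

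It would also help to list the imputation-model covariates, including whether the baseline count is among them.

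No new data or visits are needed. The cost is SAP wording, slightly more programming, and a fallback that will occasionally be used (about 2% of simulated trials at 74 per arm).

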9.6.2 Analysis of Key Secondary Efficacy Endpoints

For the first key secondary endpoint, proportion of subjects achieving eosinophilic histologic response defined as a peak esophageal eosinophil count < 15/hpf (across all available esophageal levels) at Week 24, the main analysis will be conducted based on the ITT population using the same type of method as described for the histologic response at Week 24 (the co-primary endpoint). The same summary and inferential statistics will be reported as specified for the primary analysis of the co-primary endpoint of histologic response in Section [9.6.1.3](#). Missing data and ICEs of interest will be handled via the same strategy as for the primary analysis of the co-primary endpoint of histologic response.

For the second key secondary endpoint, mean change in the endoscopic features of EoE as measured by the EoE Endoscopic Reference Score (EREFS) from baseline to Week 24, the main analysis will be conducted based on the ITT population using an ANCOVA model with treatment group, Steroid Inadequate Responders/Intolerant status (yes or no), and baseline EREFS values included in the model. The same summary and inferential statistics will be reported as specified for the primary analysis of the co-primary endpoint of change in DD in Section [9.6.1.2](#). Missing data and ICEs of interest will be handled via the same strategy as for the primary analysis of the co-primary endpoint of change in DD.

For the third key secondary endpoint, mean change in the mean adjusted histology grade score as measured by the scoring system (EoEHSS) from baseline to Week 24, the main analysis will be conducted based on the ITT population using an ANCOVA model with treatment group, Steroid Inadequate Responders/Intolerant status (yes or no), and baseline mean adjusted histology grade score values included in the model. The same summary and inferential statistics will be reported

as specified for the primary analysis of the co-primary endpoint of change in DD in Section 9.6.1.2. Missing data and ICEs of interest will be handled via the same strategy as for the primary analysis of the co-primary endpoint of change in DD.

For the fourth key secondary endpoint, mean change in the mean adjusted histology stage score as measured by the scoring system (EoEHSS) from baseline to Week 24, the main analysis will be conducted based on the ITT population using an ANCOVA model with treatment group, Steroid Inadequate Responders/Intolerant status (yes or no), and baseline mean adjusted histology stage score values included in the model. The same summary and inferential statistics will be reported as specified for the primary analysis of the co-primary endpoint of change in DD in Section 9.6.1.2. Missing data and ICEs of interest will be handled via the same strategy as for the primary analysis of the co-primary endpoint of change in DD.

For the fifth key secondary endpoint, mean change in mDSD composite score from baseline to Week 24, the main analysis will be conducted based on the ITT population using an ANCOVA model with treatment group, Steroid Inadequate Responders/Intolerant status (yes or no), and baseline mDSD composite score values included in the model. The same summary and inferential statistics will be reported as specified for the primary analysis of the co-primary endpoint of change in DD in Section 9.6.1.2. Missing data and ICEs of interest will be handled via the same strategy as for the primary analysis of the co-primary endpoint of change in DD.

For the binary endpoint (the first key secondary endpoint), a supplementary analysis using the treatment policy estimand strategy will also be conducted. All observed data will be used regardless of ICE.

For continuous endpoints (second to fifth key secondary endpoints), supplementary analyses using the treatment policy estimand strategy and a hypothetical estimand strategy to handle ICEs of rescue therapy/prohibited medication use will also be conducted. Data will be analyzed using the same ANCOVA model as described in this section.

9.6.3 Analysis of Secondary Efficacy Endpoints

End of Maintenance Phase (Week 48):

Histologic Response: The analysis of the histologic response endpoint will be conducted on the ITT population using the CMH test stratified by Steroid Inadequate Responders/Intolerant status. For treatment comparison between a CC-93538 dose and placebo, the 2-sided 95% CI for the difference in proportions using the CMH weights will be provided. Missing data will be handled via the same strategy as for the primary analysis of the co-primary endpoint of histologic response.

Mean change in DD: For the analysis of change in DD from baseline at Week 48, the baseline is defined as the last visit prior to receiving any dose of CC-93538 360 mg or placebo in the Induction Phase. The analysis of change in DD from baseline at Week 48 will be conducted using an ANCOVA model with treatment group (CC-93538 360 mg SC once weekly, CC-93538 360 mg SC once every other week, and placebo), Steroid Inadequate Responders/Intolerant status (yes or no), and baseline DD values included in the model. Point estimates for the mean difference between the treatment groups using the adjusted LS Mean changes and corresponding 95% Wald

CI will be reported. Missing data will be handled via the same strategy as for the primary analysis of the co-primary endpoint of change in DD.

[figure not shown]
In addition to the overall population, histologic response at Week 48 and change in DD from baseline to Week 48 will be analyzed in the Steroid Inadequate Responders/Intolerant subgroup. These analyses will be similar to the overall population except that the analysis will be done using the chi-square test and the ANCOVA model will not include Steroid Inadequate Responders/Intolerant status. See Section 9.6.4 for details on the hierarchical testing procedure to control the Type I error rate.

9.6.4 Control of the Type I Error Rate

A hierarchical testing procedure will be utilized to permit confirmatory assessment of the co-primary endpoints, 5 key secondary endpoints, and 2 secondary endpoints at Week 48 in the overall population. In addition, the hierarchical testing procedure includes confirmatory assessment of the co-primary endpoints and two secondary endpoints at Week 48 in the Steroid Inadequate Responders/Intolerant subgroup. The Type I error rate is controlled for multiplicity (Dmitrienko, 2013).

Figure 2 presents the schematic for the hierarchical testing procedure for the United States and other non-European Union regions. A fixed sequence test will be applied and each hypothesis will be tested sequentially at an α level of 0.05. For the 2 co-primary endpoints, both p-values need to be less than α to continue to test the next endpoint of the sequence. For this hierarchy, the result(s) will be considered confirmatory if all previously tested hypotheses in the hierarchy are statistically significant at $\alpha = 0.05$.

Figure 2: Multiplicity Adjustment for the US and Other Non-EU Regions

Abbreviations: DD = dysphagia day(s); EoE = eosinophilic esophagitis; EoEHSS = EoE histology scoring system; eos = eosinophils; EREFS = EoE Endoscopic Reference Score; hpf = high-power field; ITT = intent-to-treat; mDSD = modified daily symptom diary; SIR-I = Steroid Inadequate Responders/Intolerant; WK = week

Note: p_1 and p_2 represent the p-values for the 1st co-primary endpoint of change in DD and 2nd co-primary endpoint of histologic response, respectively.

For the EU, 2 additional endpoints in the Induction Phase will be included in the hierarchy:

- The proportion of subjects with a $\geq 50\%$ decrease in dysphagia days (DD) from baseline at Week 24
- The proportion of subjects who achieve histologic response defined as a peak esophageal eosinophil count $\leq 6/\text{hpf}$ at Week 24 and dysphagia symptom response defined as the proportion of subjects with $\geq 50\%$ decrease in dysphagia days (DD) from baseline at Week 24

Details of the hierarchy for the EU analysis will be discussed in the SAP.

9.6.5 Subgroup Analyses

To assess whether the treatment effect is consistent across various groups, subgroup analyses will be performed for the co-primary endpoints at Week 24. Treatment differences and 2-sided 95% CIs will be provided for each subgroup listed below. Forest plots for the treatment differences by subgroup will also be provided.

- 1) Steroid Inadequate Responders/Intolerant status as reported in EDC (yes versus no)
- 2) Prior history of corticosteroid use for the treatment of EoE (yes versus no)
- 3) Age group (adolescents [< 18 years] versus adults [≥ 18 years], non-elderly adults [18 to < 65 years] versus elderly adults [≥ 65 years])
- 4) Previous dilation procedure for EoE (yes versus no)
- 5) Sex (female versus male)
- 6) Region (North America versus non-North America, European Union versus non-European Union)
- 7) Presence of atopy (yes versus no)
- 8) On stable concomitant PPI regimen (yes versus no)
- 9) On stable dietary modification (eg, elimination diet for the treatment of allergy or EoE [yes versus no])
- 10) Race (white versus non-white)

9.7 Safety Analysis

All analyses of safety data will be conducted using the Safety population by treatment for the Induction Phase and by treatment and in Total CC-93538 for the Maintenance Phase. The assessment of safety will include AEs, SAEs, AEs leading to discontinuation of study treatment, changes from baseline in laboratory values and vital signs, and incidence and type of laboratory, vital signs, and physical examination abnormalities. Individual data listings will also be provided.

Adverse events will be monitored during the trial, and the data will be analyzed with respect to incidence within each treatment group as well as severity and potential relationship of the AEs to IP.

Laboratory assessments will be performed by a central laboratory. All summaries will be based on the standard International System of Units (SI) provided by the central lab. Each subject's

hematology, blood chemistry, and urinalysis values will be flagged as “low”, “normal”, or “high” relative to the normal ranges of the central laboratory.

Summary statistics of actual values and changes from baseline in vital signs will be provided by visit.

